Recruitment. Individuals with physician-confirmed RA will be targeted in this study. Patients will be recruited via physician referral from the Johns Hopkins Arthritis Center, which is directed by Co-I [name], or via IRB-approved advertisements.

Screening and Randomization:

Telephone Screen: Participants will undergo an initial screen over the phone (or in person if they are initially identified in the Arthritis Center Clinic), prior to informed consent. Participants meeting initial screening criteria will be scheduled for a subsequent screening session.

Screening Session (Session 1): At the screening session (either remote or in person), participants will complete screening measures through REDCap and an interview with study staff. Participants will also be shown a video to familiarize themselves with noxious thermal stimuli.

Eligible participants will be randomized to MB, SAV, or Sham MB, and starting in July, 2020, participants will only be randomized to SAV or Sham MB. The female to male ratio in RA is approximately 2-3:1^{71,72}, and RA is diagnosed at a higher rate in White Americans compared to African Americans.⁷³ To ensure these differences are accounted for, we will test sex and race as covariates in analyses.

Intervention Visits: Intervention sessions for each randomized condition will be one-on-one with an interventionist. Sessions (4 total) will take place via secure remote video conference (e.g., Zoom) or in the Johns Hopkins Behavioral Medicine Research Lab (BMRL) as dictated by COVID-19 conditions, and will last 20-minutes. Intervention visits will be scheduled 2 per week, so that the entire intervention will be completed in 2 weeks.

Intervention Descriptions

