Data Analysis: fMRI data preprocessing will be performed using methods previously described in our work.^{18,19} Briefly, ASL images will be combined into a single CBF volume, and motion will be corrected using filters designed to minimize perfusion-based fluctuations. After these corrections are performed, global CBF will be calculated as a voxel-wise mean from the CBF volume. All non-fMRI variables will be checked for normality, and any non-normal outcome measures will be log-transformed as appropriate. Sex is an important biological variable in chronic pain¹⁰⁹, and we will report data disaggregated by sex.

However, due to the overrepresentation of females in RA, we are not powered to test for sex differences. In addition, a priori covariates will include sex, race, medication classifiers, age, clinical pain severity, depression symptoms, and anxiety symptoms, as each has been linked to variation in RA symptoms and other rheumatic diseases.^{26,110,111} Missing data will be handled by restricted maximum likelihood. If the missing-at-random assumption is violated, multiple imputation will be considered. Two-tailed p values ($\alpha = .05$) with 95% confidence intervals will be used to evaluate statistical significance.

The functional image analysis package FSL (FMRIB Software Library, Oxford, UK) will be used for first and second level statistical analyses. Functional images derived from CBF volumes are concatenated into a 4D volume for each individual, smoothed, normalized, and coregistered onto structural images using a standard nonlinear transformation.^{112,113} Next, regional signal changes in a priori regions (lOFC, putamen, vmPFC, and NAc) are assessed in first level, with T/F statistic images Gaussianized and cluster thresholded to correct for multiple comparisons across brain voxels.¹¹⁴

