Mixed effects modeling will be used as the primary analytic strategy for the primary outcomes. In our group therapy RCT design, mixed effects models permit the modeling of cohort-level random effects, as well as heterogeneous variance/covariance matrices to account for potential alpha inflation due to cohort-level clustering. We will test regional signal change in each ROI using mixed effects models examining within-person main effects of thermal stimulus (HEAT; i.e., painful vs. warm) and skill practice (PRACTICE; i.e., rest vs. active practice in the scanner during delivery of thermal stimuli), and the between-person main effect of intervention condition (CONDITION; i.e., MB vs. Sham MB vs. SAV), as well as their requisite 2-way and 3-way interactions. Thus, the HEAT X PRACTICE X CONDITION interaction will test the extent to which CBF in each a priori corticostriatal region varies during the active practice of either Sham MB, or SAV, relative to rest. Planned comparisons will test each of the HEAT X PRACTICE 2-way interactions within intervention groups to aid in the interpretation of the 3-way interaction.

Updated Statistical Approach due to Covid-19

Due to COVID-19 restrictions, we had to drop one arm from the study (Mindful Breathing). As such, a new statistical analysis plan was developed that we detail in the next section.

fMRI Pre-Processing: Imaging analysis was conducted using Functional Magnetic Resonance Imaging of the Brain (FMRIB) Software Library (Center for FMRIB, University of Oxford, Oxford, UK) and ASL data processing toolbox. Five subjects were excluded from analysis due to detected image artifact or excessive motion. A total of 29 subjects (15 SAV group, 14 NMB) were included in the final imaging analysis. Subjects underwent 8 functional (ASL) runs during the MRI challenge session. The 8 ASL images that resulted from the runs represented combinations of two experimental conditions: Pain (nonpainful warm stimulus vs. noxious heat) and Practice (no meditation vs. meditation). These combinations occurred in the following order: 1. warm + no meditation; 2. noxious + no meditation; 3. warm + no meditation; 4. noxious + no meditation; 5. warm + meditation; 6. noxious + meditation; 7. warm + meditation; 8. noxious + meditation.

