ASL images were motion corrected using the ASL MRI MoCo Method (Wang 2012). An additional motion correction and signal outlier filtering step was included (Tan et al 2009) to account for excessive motion and corruptive signal fluctuations. ASL images were converted into absolute CBF units according to the general kinetic model. The 8 CBF images were concatenated, intensity normalized, and then smoothed with a 9mm full-width half maximum (FWHM) Gaussian kernel. The images were spatially normalized to the MNI (Montreal Neurologic Institute) standard space using a 12-parameter affine transformation and then a nonlinear transformation. Additionally, a global white matter value was calculated for each CBF image by

extracting average white matter values from FSL's MNI152 white matter mask. The global white matter value was included in statistical models as a nuisance regressor.

Statistical Approach for fMRI: A group one-sample t-test ($n = 29$) was used to determine whole-brain, pain-related regions. The two Warm+No Meditation scans were subtracted from the two Noxious+No Meditation scans and then averaged. This average residual value per subject was used as the dependent measure included in the one-sample t-test.

Multiple regression analyses investigated the relationship between pain intensity/unpleasantness ratings and CBF during the Noxious condition. The 1st regressor consisted of the mean difference between the 2 Noxious+no Meditation scans vs Noxious+Meditation scans. The 2nd regressor included the percent change in subjects' pain intensity ratings from the Noxious+no Meditation to the Noxious+Meditation scans. The 3rd regressor included the percent change in the subjects' pain unpleasantness ratings from the Noxious+no Meditation to the Noxious+Meditation scans. All 3 regressors were orthogonalized to each other.

Because this was a proof-of-concept pilot mechanistic trial with a limited sample size, we set voxelwise threshold to 2.3, cluster corrected at $p=0.05$ (Worsley et al., 1992), in line with previous meditation-based imaging studies of similar size (Zeidan et al., 2015).

d. Early stopping rules.

We will report all adverse events and evaluate on a case-by-case basis whether the occurrence of a particular adverse event has implications for discontinuing the study to ensure participant safety and well-being.

8. Risks

a. Medical risks, listing all procedures, their major and minor risks and expected frequency.

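### The updated analysis section is undated, was written after image exclusions were known, and sets out other analyses in place of the planned ROI model without a SAV-versus-sham test

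*Combined protocol and SAP*

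**What the plan says.** Section 7a makes brain function in the corticostriatal circuits the primary outcome. Under Data Analysis, Section 7c gives mixed effects modelling as the main approach for the primary outcomes. Regional signal change in each ROI (lOFC, putamen, vmPFC, NAc) is modelled with HEAT, PRACTICE, CONDITION and all their interactions, at two-tailed alpha 0.05. The statistic images are to be "cluster thresholded to correct for multiple comparisons across brain voxels", with no voxelwise value given.

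Section 4a dates the loss of the MB arm: "starting in July, 2020, participants will only be randomized to SAV or Sham MB". The document itself is dated July 28, 2022.

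The updated part of Section 7c gives the dropped arm as its reason and continues: "As such, a new statistical analysis plan was developed that we detail in the next section". What follows is retrospective, beginning "Imaging analysis was conducted using Functional Magnetic Resonance Imaging of the Brain (FMRIB) Software Library". It reports that artifact or motion had removed five people, and gives the numbers left: "A total of 29 subjects (15 SAV group, 14 NMB) were included in the final imaging analysis". It then describes two analyses:

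- a one-sample t-test (n = 29) on noxious minus warm scans, both without meditation, to locate pain-responsive regions across the whole brain;
- multiple regressions relating CBF during noxious heat to percent change in pain intensity and unpleasantness ratings, alongside a regressor for the no-meditation versus meditation difference.

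On the threshold it says: "Because this was a proof-of-concept pilot mechanistic trial with a limited sample size, we set voxelwise threshold to 2.3". A correction at cluster level, p = 0.05, is applied on top of this. The section also appeals to precedent, calling the choice "in line with previous meditation-based imaging studies of similar size".

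**The concern.** An analysis plan protects the error rate only if it can be shown to predate sight of the results. This section calls itself a new statistical analysis plan. Yet it was written when exclusions and group sizes were known, and it says nothing about when its choices were made or what had been seen by then.

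The document therefore holds two accounts of how the primary outcome is analysed. One was written in advance and compares the randomised groups. The other was written up afterwards and, as described, does not compare them. Nothing says whether the first still stands. That leaves a route to selective reporting, and the trial's mechanistic conclusion could come to rest on maps and pain correlations instead of the randomised contrast for which the study was sized.

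**Working it through.** **1. When the section was written.** The counts need completed image quality control.

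- Subjects with imaging: 29 + 5 = 34, if the five are the only imaging exclusions. Share excluded: 5/34 = 14.7%.
- Analysed against planned: 29/40 = 72.5%.
- The split is given by named arm, 15 and 14. NMB is not defined; I take it to be the sham arm.

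The arm was dropped in July 2020 and the document is dated July 28, 2022, about two years later. The new plan has no date within or before that interval.

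**2. What losing MB does to the planned model.** HEAT and PRACTICE have two levels each. The degrees of freedom of the HEAT x PRACTICE x CONDITION interaction are:

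- three arms: (2 − 1)(2 − 1)(3 − 1) = 2
- two arms: (2 − 1)(2 − 1)(2 − 1) = 1

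The model survives. In each ROI the interaction becomes a single contrast: the practice-minus-rest change in the noxious-minus-warm difference, SAV minus Sham MB. The updated section lists eight runs, two in each of the four HEAT-by-PRACTICE cells, so the data for it exist: 29 x 8 = 232 scans. The forward-looking text had also been partly adapted to two arms. It targets 20 per group and 40 in total, and it explains the interaction in terms of Sham MB or SAV, although its CONDITION definition still lists MB.

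**3. What the update describes instead.**

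| | Planned ROI model | One-sample t-test | Regressions |
|---|---|---|---|
| Scans | all HEAT-by-PRACTICE cells | no-meditation only | noxious only |
| Search region | four a priori ROIs | whole brain | not stated |
| SAV-versus-sham term | yes | no | none described |

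The t-test cannot speak to practising either skill, because no practice scan enters it. The three listed regressors include no arm indicator.

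**4. The threshold.** Read as Z, 1 − Φ(2.3) = 0.0107 one-sided per voxel, before cluster correction at p = 0.05. The earlier text has no voxelwise value, so there is nothing to compare it with.

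**5. What the planned comparison can deliver at 15 and 14.** The plan states over 80% power at 17 per group. It gives no effect size or SD, so that figure cannot be reproduced. Taking exactly 80%, a simple two-sample comparison and two-sided 0.05, the implied standardised effect is

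d = (1.960 + 0.842) x √(2/17) = 0.96 (0.99 with the noncentral t).

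At 15 and 14, power = Φ(0.96/√(1/15 + 1/14) − 1.960) ≈ 0.73, by either method. Across other alpha levels and one- or two-sided tests the t-based figure runs from 68% to 74%. This is indicative only: the plan's input contrast was MB versus sham, not SAV versus sham.

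**The case against.** The best defence is that the section hides nothing. Its tense, exclusions and final numbers are in plain view, and the earlier mixed model remains in the document, so a careful reader can see the departure. Time of writing is also not time of choice: the plan may have been settled soon after July 2020 and only written up later. Knowing motion exclusions and group sizes is not knowing contrast results, and Section 4c says investigators are blind to assignment. The one-sample t-test serves to locate pain-responsive regions, so it need not compete with the mixed model, and t-tests were already mentioned under Sample Size Estimation.

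Much of this stands, and it rules out several stronger readings that a reader might infer:

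- *That the plan offers these results as confirmatory.* It does not. It calls the trial a proof-of-concept pilot and disclaims power for efficacy. The alpha of 0.05 and the power statement sit in the earlier text.
- *That the tests and threshold were chosen after seeing results.* The documents neither show nor exclude this.
- *That 2.3 was loosened to suit the number of scans obtained.* The text says only that the sample was limited, which also fits the planned 20 per group. It adds pilot status and precedent, and no stricter earlier value exists.
- *That the regressions were pooled and whole-brain.* Only the t-test is described that way.

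What the defence does not supply is a date, a statement of what had been seen, a reason why losing one arm calls for different analyses, or a SAV-versus-sham test. The blinding statement is not tied to the date of the new plan.

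**Conclusion.** The point holds as a failure to demonstrate prespecification, combined with an unexplained departure from the main analysis of the primary outcome. The updated section was written after 5 of an apparent 34 scanned subjects had been excluded and the 15 and 14 were known. Its stated reason removes one level of one factor and does not account for the change of method. As described, it contains no test of the randomised comparison. Its p-values should therefore be read as exploratory.

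I put no figure on false-positive inflation, because the documents do not say how many alternatives were open. The conclusion assumes that the text is complete on this point and that NMB is the sham arm. A dated record fixing the new plan before group results were seen would answer the timing concern, but not the missing between-group test.

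**What to change.** In the updated part of Section 7c:

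1. State when the new plan was fixed, and which data (scan quality, allocation, ROI values, maps, pain ratings) had been seen by then and by whom.
2. Label the whole-brain t-test and the pain-rating regressions exploratory, with the 2.3 threshold reported as part of that.
3. State that the ROI mixed model (HEAT x PRACTICE x CONDITION in lOFC, putamen, vmPFC and NAc) remains the primary analysis, with CONDITION reduced to SAV versus Sham MB at two-tailed 0.05. Report it first whatever its result, and base the primary conclusion on it.

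The cost is some wording and one model that was already planned, on scans already acquired. The map and pain-correlation results become hypothesis-generating. With 15 and 14 analysed, the primary comparison probably has less power than the plan states (about 73% under the assumptions above), so a null result should be reported with its confidence interval and not read as absence of an effect.

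### The updated fMRI analysis contrasts rest runs with later meditation runs, states no SAV-versus-sham test, and leaves open whether the mixed model containing that test is kept

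*Combined protocol and SAP*

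**What the plan says.** Section 7c contains two layers of analysis text.

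The Data Analysis text looks forward. It states: "Mixed effects modeling will be used as the primary analytic strategy for the primary outcomes". The between-person factor is listed as "CONDITION; i.e., MB vs. Sham MB vs. SAV", and "the HEAT X PRACTICE X CONDITION interaction will test the extent to which CBF in each a priori corticostriatal region varies". The rest of that sentence names only Sham MB and SAV as the practised skills.

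The section headed Updated Statistical Approach due to Covid-19 explains that the mindful breathing arm was dropped and that "a new statistical analysis plan was developed that we detail in the next section". It is written in the past tense and gives final counts: five subjects excluded, 29 analysed (15 SAV, 14 NMB). It gives the run order as "These combinations occurred in the following order: 1. warm + no meditation; 2. noxious + no meditation", with the same pair repeated as runs 3 and 4, and then "5. warm + meditation; 6. noxious + meditation; 7. warm + meditation; 8. noxious + meditation".

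Two analyses follow. A one-sample t-test on all 29 subjects uses rest runs only: "The two Warm+No Meditation scans were subtracted from the two Noxious+No Meditation scans and then averaged". A multiple regression relates pain ratings to CBF: "The 1st regressor consisted of the mean difference between the 2 Noxious+no Meditation scans vs Noxious+Meditation scans". Its second and third regressors are percent changes in intensity and unpleasantness ratings over the same runs. The only nuisance term named is global white-matter CBF. In the update the arms appear only as counts.

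The Abstract (Section 1) and the Sample Size Estimation in Section 7c both frame the question as a difference between an intervention and Sham MB.

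**The concern.** Every rest run came before every meditation run, so practice and elapsed time move together. A subject's CBF can change between the two halves of the session because of the skill, time in the scanner, or repeated heat. A within-person contrast over these runs cannot separate these causes. The randomised comparison can: if order effects are similar in both arms, they cancel in SAV minus sham.

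The update states no such comparison. The mixed model has one, but its status is not given, and its CONDITION list still names an arm that is no longer randomised. A reader following the update alone has no randomised test of the trial's question. A pooled or within-arm change could then be reported as a meditation effect when order created it, or a real effect could be hidden by order.

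**Working it through.** **The plan's own figure.** Sample Size Estimation gives over 80% power at 17 per group. It comes from imaging power software and a contrast whose effect size and SD are not printed, so it cannot be reproduced. The argument below does not use it.

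**Inputs.** Run positions from the update: warm rest 1, 3; noxious rest 2, 4; warm meditation 5, 7; noxious meditation 6, 8. Analysed: 15 SAV and 14 NMB, with NMB taken to be Sham MB (assumption; the label is not defined). Two-sided 5% level, from Data Analysis.

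**1. Lag in each contrast (difference in mean position).**
- Noxious meditation minus noxious rest: (6+8)/2 − (2+4)/2 = 7 − 3 = 4 positions, or two noxious exposures.
- Noxious rest minus warm rest (the one-sample test): 3 − (1+3)/2 = 3 − 2 = 1 position.
- HEAT x PRACTICE within an arm: (7 − 3) − (6 − 2) = 0. Linear drift common to warm and noxious runs cancels; drift specific to noxious heat does not.

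**2. Could a run-position term separate the two?** Over the four noxious runs, practice (0, 0, 1, 1) and position (2, 4, 6, 8) correlate 0.89. A linear run term is estimable, but the variance of the practice estimate rises from 1.0 to 5.0 (in units of the run-error variance), a factor 1/(1 − 0.80) = 5. Over all eight runs with HEAT in the model it rises from 0.5 to 2.5, again a factor of 5.

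**3. What drift could do (illustration only).** The documents give neither size nor direction for drift, and they do not state a test of the mean of regressor 1. Suppose such a test were run on 29 subjects, practice did nothing, and total drift were a given multiple of the SD of the within-person change (assumption). The noncentral t gives:

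| Drift (SD) | 0 | 0.2 | 0.4 | 0.6 |
|---|---|---|---|---|
| Rejection, n = 29 | 5% | 18% | 55% | 88% |

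With equal drift in both arms, the two-sample test of SAV minus sham stays at 5% (simulation: 4.8% to 5.1%). If drift differs between arms by 0.1, 0.2 or 0.4 SD (assumption), it rejects 6%, 8% or 18%.

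**4. Precision of the between-arm test.**
- Standard error in SD units: √(1/15 + 1/14) = 0.372 between arms; 1/√29 = 0.186 pooled.
- 95% half-width: 2.052 × 0.372 = 0.76; pooled 2.048 × 0.186 = 0.38.
- Detectable effect at 80% power: 1.08 between arms; 0.54 pooled. At a level of 0.05/4, if the four regions are corrected for, the between-arm figure is about 1.32.
- Three-way contrast: with independent run errors, the four-cell contrast has twice the variance of the noxious-only one. The detectable effect is 1.080 × √2 = 1.53 noxious-only SDs and the half-width 0.762 × √2 = 1.08. Positive correlation among a subject's runs beyond a constant subject effect could make both smaller.

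**The case against.** The strongest reply is that the between-arm test is already printed. The mixed model is called primary, and its interaction sentence lists only Sham MB and SAV, which suggests it was edited after the arm was dropped and is still in force. That is a fair reading. The announcement of a new plan points the other way, and nothing settles it. A reader might infer that the mixed model was abandoned; the documents do not say so.

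Nor should the model be credited with too much. It has no run term, and its PRACTICE main effect is as confounded as regressor 1. Only its between-arm interactions remove order effects, and only where those are similar in both arms.

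Second, the update describes its regressions as relating ratings to CBF and does not say that the mean of regressor 1 is tested. This stands. A reader might take 18%, 55% or 88% as the trial's false-positive rate. They are not: they combine an assumed drift with an unstated test, and they do not apply to the rest-only test, the rating slopes or the cluster-corrected map.

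Third, rest-first order has a reason: Section 4a tells sham participants to keep meditating, once started, until the experiment ends. That explains the order in that arm and makes the comparison arm the natural control.

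Fourth, intensity normalisation and the white-matter covariate may reduce global drift. They do not address regional or heat-specific change over runs.

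Finally, one might infer either that everything in the update is confounded or that the other two analyses are untouched. Neither is right. The one-sample contrast is free of the rest-before-meditation order but carries one run position of drift. The rating slopes are unbiased if drift is equal in every subject; if habituation varies between people and moves both ratings and CBF, a slope can arise without a meditation effect.

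**Conclusion.** The point holds as a gap in the stated analysis, not as a demonstrated bias. If the update is the whole analysis, no stated test addresses a difference from Sham MB, and any pooled or within-arm rest-to-meditation change in CBF is confounded with order through a lag of 4 run positions. If the mixed model is kept, the between-arm test exists and what is missing is the statement that it is primary, with a corrected CONDITION list. The documents do not show which case applies.

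The size of any drift, and so of any bias, is unknown. The conclusion rests on the printed run order having applied to every subject and on NMB being the Sham MB arm. It should be dealt with before results are interpreted, and it needs no new data.

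**What to change.** 1. State that the HEAT x PRACTICE x CONDITION model, with CONDITION reduced to SAV and Sham MB, remains the primary test in the a priori regions (lOFC, putamen, vmPFC, NAc), and correct the list that still names MB. If the model was withdrawn, report it all the same as the original prespecified primary analysis and disclose when and why it was replaced. It was printed prospectively, so it should not be relabelled post hoc.
2. As supporting evidence, report the SAV-minus-sham difference in noxious rest-to-practice CBF change with its 95% confidence interval. Note that Sample Size Estimation prespecified the between-group hypothesis but that neither layer of the plan states this exact contrast. Say that it removes order effects only where they are similar in both arms.
3. Add: *All no-meditation runs preceded all meditation runs; pooled or within-arm rest-to-meditation changes in CBF or ratings, and their association, are descriptive and may reflect order.*
4. Reconcile Section 4a, which describes thermal blocks as pseudorandomly interleaved, with the fixed warm-then-noxious sequence in the update. The cancellation of linear drift in HEAT x PRACTICE depends on that sequence.

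The cost is re-running contrasts on existing scans, some added wording, and the lower precision shown above. A null between-arm result must be given with its interval and not read as no effect.

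### The updated post-COVID analysis contains no SAV versus Sham MB contrast, and no sentence says whether it replaces or supplements the mixed model still labelled primary

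*Combined protocol and SAP*

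**What the plan says.** All of this is in section 7c of the combined protocol and SAP.

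- **Data Analysis.** "Mixed effects modeling will be used as the primary analytic strategy for the primary outcomes". The model has two within-person factors, HEAT and PRACTICE, and "the between-person main effect of intervention condition (CONDITION; i.e., MB vs. Sham MB vs. SAV"), with all interactions. The next sentence describes the three-way interaction as testing how blood flow (CBF) in each a priori region "varies during the active practice of either Sham MB, or SAV, relative to rest". The factor definition therefore has three arms, while the interpretation has two.
- **Updated Statistical Approach due to Covid-19.** After noting that MB was dropped: "As such, a new statistical analysis plan was developed that we detail in the next section".
- **fMRI Pre-Processing.** "A total of 29 subjects (15 SAV group, 14 NMB) were included in the final imaging analysis". NMB is not defined; I read it as the Sham MB arm. Eight runs are listed in a fixed order. The first four are without meditation and the last four with it, and the list ends "4. noxious + no meditation; 5. warm + meditation; 6. noxious + meditation; 7. warm + meditation; 8. noxious + meditation".
- **Statistical Approach for fMRI.** Two analyses are described. The first is a one-sample t-test on all 29 participants, using noxious minus warm scans without meditation. The second is the set of regressions: "Multiple regression analyses investigated the relationship between pain intensity/unpleasantness ratings and CBF during the Noxious condition". The first regressor is defined so: "The 1st regressor consisted of the mean difference between the 2 Noxious+no Meditation scans vs Noxious+Meditation scans". The second and third are percent changes in pain intensity and in unpleasantness.

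**The concern.** The design is a randomised comparison. The Abstract asks about activation relative to Sham MB, the Overview of Study in section 4a describes a two-arm trial of SAV and Sham MB, and Sample Size Estimation says the study is powered for group differences in corticostriatal activation. A plan introduced as new should show where that comparison is made, and the updated section does not.

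Two things are at stake. First, if the updated section is the operative plan, the randomised effect on the primary outcome goes unestimated. Separate findings within each arm, or associations across participants, would not replace it. Second, the average change from rest to practice under noxious heat (regressor 1) compares earlier runs with later ones, so it is open to effects of time in the scanner.

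The updated section is written in the past tense, with exclusions and final numbers known. A reader therefore cannot tell which of the two sets of analyses was meant to answer the primary question.

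**Working it through.** **1. Search for an arm term in the updated section.**

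| Analysis | Scans used | Arm term or arm contrast |
|---|---|---|
| One-sample t-test, n = 29 | No-meditation only | None |
| Regressor 1 | Noxious, rest versus practice | None |
| Regressor 2 | Change in pain intensity | None |
| Regressor 3 | Change in unpleasantness | None |

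The count is 0 of 2 analyses and 0 of 3 regressors. The t-test cannot show an effect of practising either skill, because it uses no practice scans. The text does not say whether the regressions were fitted across arms or by arm.

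**2. Search for a statement of status.** No sentence in the updated section mentions the mixed model, and none says that it is kept, replaced or made secondary. The words updated and new point to replacement. The surviving primary label and the interaction sentence already worded for two arms point to retention.

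**3. Time in the scanner.** Number the runs 1 to 8. Noxious runs at rest are 2 and 4, and noxious runs in practice are 6 and 8. Suppose the signal drifts by b per run.

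- Regressor 1: mean run position (6 + 8)/2 − (2 + 4)/2 = 7 − 3 = 4. A linear drift contributes 4b in size, and a step between runs 4 and 5 enters in full.
- HEAT × PRACTICE within a participant, (noxious − warm) in practice minus (noxious − warm) at rest: [(6 + 8)/2 − (5 + 7)/2] − [(2 + 4)/2 − (1 + 3)/2] = (7 − 6) − (3 − 2) = 0. A linear drift cancels. A step between runs 4 and 5 also cancels, since it adds equally to warm and noxious runs.
- A drift proportional to the square of the run number does not cancel: [(36 + 64)/2 − (25 + 49)/2] − [(4 + 16)/2 − (1 + 9)/2] = 13 − 5 = 8.

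The arm comparison also removes any time effect that both arms share.

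**4. The plan's own sample size figure.** Sample Size Estimation gives over 80% power at 17 per group, corrected for multiple comparisons, from imaging power software and MB versus sham data. No effect size or SD is given, so the figure cannot be reproduced. As an illustration only, a plain two-sample t-test at two-sided 0.05 has 80% power at 17 per arm for a standardised difference of 0.99. At 15 versus 14 its power for that difference is 73%.

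**5. Precision of the missing contrast.** Inputs are 15 and 14 participants and 15 + 14 − 2 = 27 degrees of freedom, in units of the between-participant SD of the contrast.

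Half-width = t(1 − α/2, 27) × √(1/15 + 1/14), and √(1/15 + 1/14) = 0.3716.

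- α = 0.05: 2.052 × 0.3716 = 0.76 SD.
- α = 0.05/4 = 0.0125: 2.676 × 0.3716 = 0.99 SD.

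**The case against.** The strongest reply is that the arm comparison is already in the plan. The mixed model is still labelled primary, its three-way interaction is a between-arm test, and the sentence interpreting it names only Sham MB and SAV. This stands as far as it goes: a reader might infer that the trial has no planned arm comparison at all, and the documents do not support that. They also do not confirm that the model was kept, because a later passage introduces a new plan without mentioning it.

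A second reply is that the Abstract also states a purpose about mechanisms of pain relief, which the regressions address. That is fair: the arm contrast is a main purpose of the trial, not its only one.

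A third concerns time effects. A reader might infer that only the arm comparison can remove them, or that the regression findings are scanner-time artefacts. Neither follows. The within-arm HEAT × PRACTICE contrast, which Data Analysis already plans, cancels a step or linear drift. The updated section intensity-normalises the images and uses a per-image white-matter value as a nuisance regressor, and both may reduce global drift. A shift equal in everyone would not by itself create the associations tested by regressors 2 and 3.

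Finally, the pilot label is offered in the updated section to justify the voxelwise threshold. It is not offered as a reason to leave out the randomised comparison.

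**Conclusion.** The point holds, and its weight depends on which plan governs. If the updated section governs, the trial does not estimate its randomised effect on the primary outcome, and this must be corrected. If the mixed model governs, the defect is an obsolete MB level and analyses without a stated status.

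The finding rests on reading the text, where the count of arm contrasts in the updated section is zero; no assumed effect size enters it. The half-widths of 0.76 and 0.99 SD assume a two-sample comparison of one contrast per participant, complete data on 15 and 14 participants, and NMB meaning Sham MB. The 73% power figure is illustrative and carries no weight in the conclusion.

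A reader might also infer that the regressions pooled the arms, or that the mixed model was deliberately abandoned. The documents are silent on both.

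**What to change.** 1. State which analysis governs the primary outcome: the mixed model, or the plan in the updated section.
2. Either way, report one SAV versus Sham MB contrast in the a priori regions named in Data Analysis (lOFC, putamen, vmPFC, NAc). This is the HEAT × PRACTICE × CONDITION estimate with a two-level CONDITION and its 95% confidence interval. One way to obtain it is the arm difference in each participant's (noxious − warm) in practice minus (noxious − warm) at rest.
3. Say whether the white-matter regressor is kept. It varies by run, so with it in the model, or with missing runs, the model estimate need not equal that simple difference exactly.
4. State how multiplicity over regions is handled.
5. If the mixed model was dropped and the contrast is added now, label it as specified after the analysis set was known.
6. Label the one-sample t-test and the regressions secondary or descriptive, and say whether the regressions were fitted across arms or by arm.

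The cost is SAP wording, extraction of mean CBF in four regions (the updated section describes none), and one model per region on existing scans. No new participants or procedures are needed. The drawback is precision: with half-widths of 0.76 to 0.99 SD, a non-significant arm difference could not be reported as evidence of no difference.
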